5. RISKS

a. Potential Risks

i. Investigational devices

The device being used is a commercially available wearable technology (the Apple Watch); it has not been shown to have association with any significant risk to the user.

ii. Investigational drugs

Not applicable

iii. Commercially available drugs, biologics, reagents or chemicals

Not applicable

iv. Procedures

The study does not include any investigational procedures. For Cohort 1, patients will be using the Apple Watch daily for 2-6 weeks prior to their spine surgery and for 12 months following surgery. For Cohort 2, patients will be using the Apple Watch daily for 2-3 weeks. The entirety of the clinical care that patients will be outside the purview of this study.

v. Radioisotopes/radiation-producing machines

Not applicable

vi. Physical well-being

The Apple Watch has not been linked to any adverse physical health effects.

vii. Psychological well-being

The device will give patients feedback on their activity. This may have positive and motivating impact on patients; however, we acknowledge that it may also negative psychological effects. The degree of the latter risk is unknown and will be monitored throughout the trial, so that it may be addressed. At each time point, patients fill out the health-related quality of life questionnaires that address aspects of anxiety and depression, so we can assess whether the Apple Watch itself is having a detrimental effect on our patients.

viii. Economic well-being

Not applicable

ix. Social well-being

Not applicable

x. Overall evaluation of risk

Low

b. International Research Risk Procedures

Not applicable

c. Procedures to Minimize Risk

For Cohort 1, we will check in with patients throughout the study period in person (4-6 weeks, 3 months, 6 months, and 12 months post-operatively); these check-in meetings will include detecting any negative effects of the study on the patient. Any unexpected hazards will be reported to the IRB, and the patient will be removed from the study.

For Cohort 2, the study is only 2-3 weeks; however, participants will be able to contact study coordinator at any point to report any negative effects of the study on the patient.

Any unexpected hazards will be reported to the IRB, and the patient will be removed from the study.

The greatest risk to patients in this study will be confidentiality of identifiable information. All electronic devices (e.g., computers, hard drives, thumb drives, etc.) that contain identifiable patient information will meet Stanford School of Medicine security standards; additionally, the devices will be password-protected and encrypted. The patient's activity data will be downloaded to Stanford Research IT-approved Google Firebase storage. All data will be stored per approved Research IT / DRA protocol. No data will be shared with industry partner providing part of the funding.

d. Study Conclusion

For Cohort 1, as participants reach the 12-month study period, we will conduct ongoing analysis of the data. If we observe clear statistically significant and clinically significant superiority in one group, the study will be terminated prior to the projected total participant population has been enrolled. If there are no such differences noted, the study will terminate after the all patients have had their 12-month postoperative visit, likely June 2022. We do not expect adverse effects but will be able to identify them at postoperative visits (4-6 weeks, 3 months, 6 months, and 12 months post-operatively) and intervene if needed.

For Cohort 2, we will conduct ongoing analysis of the data. If we observe clear statistically significant and clinically significant changes, the study will be terminated prior to the projected total participant population has been enrolled. If there are no such differences noted, the Cohort 2 will terminate after all patients have completed the study, likely August 2021.

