1. PURPOSE OF THE STUDY

a. Brief Summary

For patients who undergo spine surgery or are experiencing back pain, mobilization is an important factor in long-term medical and psychological wellbeing. Unfortunately, there is currently no established objective method such that surgeons can track their patients' mobilization progress postoperatively. We hypothesize the ability of the patient to be able to track their own activity and discuss with their surgeon objective mobilization goals will not only help patients achieve empowerment in their own care but also improve their overall satisfaction and self-reported outcomes. The purpose of this study is to test our hypothesis using the most prevalent commercially available wearable technology, the Apple Watch.

b. Objectives

In this study, we will address the following questions:

1. Is it feasible for spine patients to wear the leading commercially available device (specifically, the Apple Watch) before and after spine surgery to assist with their spine care?
2. Do objective patient metrics (steps, distance traveled, max HR achieved) obtained from this commercially available device directly correlate with subjective patient reported outcome measures (PROMs) for spine surgery patients?
3. Do we see a significant change in objective outcome metrics before and after spine surgery?
4. Are patients more satisfied with their spine care as a result of using the Apple Watch in our practice?

c. Rationale for Research in Humans

The purpose of this study is to assess the efficacy of using a commercially available wearable activity monitor (the Apple Watch) in the postoperative care of patients undergoing spine surgery.

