Our protocol does not change the standard of care for any patient. It provides a supplementary intervention for half of our patients. The intervention is using a wearable activity monitor device (the Apple watch), which is a minimal risk.

c. Use of Deception in the Study

Deception will not be used.

d. Use of Audio and Video Recordings

Audio or video recording will not occur.

e. Alternative Procedures or Courses of Treatment

Standard of care will not be withheld. Our study does not involve alternative procedures or treatments.

f. Will it be possible to continue the more (most) appropriate therapy for the participant(s) after the conclusion of the study?

All patients will undergo standard of care for their spine surgery before, during, and after the study.

g. Study Endpoint(s)

For Cohort 1, the study endpoint will be 12 months postoperatively. Following enrollment during the pre-operative visit, we will see patients in clinic during their standard postoperative visits, at 4-6 weeks, 3 months, 6 months, and 12 months post operatively. All patients will complete the Stanford Spine quality of life questionnaires, as per the standard of care, at all postoperative visits. Patients with the Apple Watch will also fill out a paper questionnaire assessing satisfaction with the Apple Watch (all questions are included in attachment).

As participants reach the 12-month study period, we will conduct ongoing analysis of the data. If we observe clear statistically significant and clinically significant superiority in one group, the study will be terminated prior to the projected total participant population has been enrolled. If there are no such differences noted, the Cohort 1 will terminate after the all patients have had their 12-month postoperative visit, likely July 2023.

For Cohort 2, the study endpoint will be 2-3 weeks after enrollment and Apple Watch setup. If we observe clear statistically significant and clinically significant changes, the study will be terminated prior to the projected total participant population has been enrolled. If there are no such differences noted, the Cohort 2 will terminate after all patients have completed the study, likely August 2021.

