Vulnerable subjects are not being selectively recruited for this study. Due to the study design, children and decisionally impaired individuals will be excluded from our study. It is possible that other types of vulnerable individuals would be included though not through targeting/solicitation (pregnant women, economically or educationally disadvantaged, homeless people, employees, and students). We will ensure that these individuals understand the voluntariness of the study and will assess that overall benefits outweigh risks of participation. All participants will be provided phone number and email address for the study coordinator whom they can contact at any point with any issues that may arise. If at any point the risks become greater and/or patients indicate no longer wanting to participate, we will take steps to ensure each individual's rights and welfare first and, if appropriate, discontinue their participation in the study. We will communicate with the IRB immediately about any issues that arise in regards to the vulnerable individuals.

d. Rationale for Exclusion of Certain Populations

Children are not included for several reasons. First, assessment of behavioral modification using WAM postoperatively in spine patients has not been studied via a trial in any population. We need to establish an understanding with an adult population first to better understand the full scope of risks and benefits before considering exposing children to the potential risks of this type of study. Second, a better assessment of commercially available WAMs use amongst children is needed to understand applicability of this research question to pediatric spine patients. Lastly, the neurosurgery faculty in this study operate primarily on adult patients, who have a much higher prevalence of spine disease than the pediatric population.

e. Stanford Populations

These populations are not being targeted by our study; however, it is possible that they will be recruited into the study if they meet eligibility criteria. We estimate that less than 10 percent of enrolled patients will be lab personnel, employees, and/or students.

f. Healthy Volunteers

All participants will have a spine pathology for which they will undergo surgery for Cohort 1 or back pain for which they will undergo standard treatment for Cohort 2. Healthy volunteers are not targeted for this study.

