6. BENEFITS

We posit that patients with spine pathology who undergo surgery or are experiencing back pain will improve their physical activity level and feel more satisfied with their quality of life when wearable activity monitors are used to provide feedback on physical activity and when such data is used to initiate discussions about activity with their spine surgeon. Our hope is that using a commercially available device will make the results of our study applicable to future patients who may also have the Apple Watch (or other commercially available activity monitors).

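### The physical-risk assessment covers the Watch but not the extra mobilisation it is meant to produce, and the scheduled harm checks depend on attributing events to the study

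*Protocol*

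**What the plan says.** **Physical risk.** Section 5.a.vi of the protocol consists of one sentence: "The Apple Watch has not been linked to any adverse physical health effects". Section 5.a.i says of the device that "it has not been shown to have association with any significant risk to the user". Section 2.b takes the same view: "The intervention is using a wearable activity monitor device (the Apple watch), which is a minimal risk".

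**What is being tested.** The hypothesis in 1.a concerns "the ability of the patient to be able to track their own activity and discuss with their surgeon objective mobilization goals". Section 6 expects that patients "will improve their physical activity level and feel more satisfied with their quality of life when wearable activity monitors are used to provide feedback".

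**What is known about it.** In explaining why children are excluded, 4.d states that "assessment of behavioral modification using WAM postoperatively in spine patients has not been studied via a trial in any population", and that adults should be studied first so that risks and benefits are better understood.

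**Psychological risk.** Section 5.a.vii names the activity feedback as a possible source of psychological harm, calls the degree of that risk unknown, and assigns the quality-of-life questionnaires at each time point to watch for it.

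**Harm detection.** Section 5.c sets in-person Cohort 1 check-ins at 4-6 weeks and at 3, 6 and 12 months after surgery, which are to include picking up unwanted effects that the study has on the patient. Section 5.d adds: "We do not expect adverse effects but will be able to identify them at postoperative visits". By 2.a, all Cohort 1 patients follow this visit schedule. Cohort 2 harms rest on participants contacting the coordinator.

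**The concern.** The risk section evaluates an object, while the trial tests a behaviour change. That a consumer watch is harmless to wear says nothing about whether prompting patients to move more before and after spine surgery has physical consequences, good or bad. The protocol applies the right reasoning to psychological risk in the very next item and does not apply it to the physical domain, which is the one the intervention is designed to change.

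The second problem is how harms are found. A check for effects of the study asks someone to decide cause before anything is written down. In a comparison of Watch with no Watch, patients know which arm they are in. A fall or a pain flare in a Watch patient can be linked to the activity feedback, whereas the same event in a control has no study exposure to be linked to. In either arm the event can be ascribed to the operation and left unrecorded.

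At stake is the main advantage of randomising: the control arm shows the background rate of physical events after surgery, but only if events are sought in the same way in both arms.

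**Working it through.** The protocol states no harm rate, and none of its figures bears on this point, so the check is mainly a comparison of sections.

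**Step 1: what each risk statement covers.**
- 2.b, 5.a.i and 5.a.vi: the Watch as a device.
- 1.a and 6: feedback and "discuss with their surgeon objective mobilization goals", with more physical activity as the expected result.
- 5.a.vii: the feedback, but only for its psychological effect.
- 4.d: the behavioural approach as a whole, described as untested.

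No section assesses the physical effect of the intended extra activity.

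**Step 2: is detection scheduled?** Yes. Sections 5.c and 5.d give four dated post-operative visits, and 2.a brings both Cohort 1 arms to them.

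**Step 3: is detection defined alike for both arms?** No. Section 5.c ties detection to effects of the study. Section 5.d speaks of adverse effects more generally. Neither names a physical event, provides a form, or says that the same questions are put to both arms. Section 4.a gives controls neither Watch nor app, and 5.a.iv places clinical care outside the study. A surgical explanation therefore takes an event out of view under the 5.c wording.

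**Step 4: what could symmetric counting show at this size?** The input from section 4.a is n = 100 per arm. The control rates p1 of 2%, 5% and 10% are assumptions, as is a doubling to p2 = 2 × p1, with two-sided alpha 0.05. With p̄ the mean of p1 and p2:

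z = [ (p2 − p1)√n − 1.96 √(2p̄(1 − p̄)) ] / √( p1(1 − p1) + p2(1 − p2) ), and power = Φ(z).

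For 5% against 10%: (0.05 × 10 − 1.96 × 0.3725) / 0.3708 = −0.62, so power is about 27%.

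| Assumed control rate | Doubled rate | Power |
|---|---|---|
| 2% | 4% | about 13% |
| 5% | 10% | about 27% |
| 10% | 20% | about 51% |

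If no event of a given kind were seen among 100 Watch patients, the one-sided 95% upper bound would be 1 − 0.05^(1/100) = 2.95%. That bound is meaningful only if every such event was looked for. If events are filtered by attribution first, a zero count bounds only the attributed events.

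A between-arm comparison would therefore be descriptive. These figures limit what the fix can deliver; they do not decide whether the wording is sound.

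**The case against.** The strongest opposing case has four parts.

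- **Harm checks exist.** A reader might infer from 5.a.vi that no collection of physical harms is scheduled. The documents do not support that: 5.c and 5.d set four visits attended by both arms, and 5.c sends unexpected hazards to the IRB. This part stands in full. The weakness is in what is asked, not in whether or when.
- **4.d and 5.a.vi do not contradict each other.** One gives a reason for studying adults before children; the other is a statement about the Watch. Both can be true. This also stands. They differ in scope, and the gap between them is the finding. Nor does the protocol claim that physical risk is nil, since 5.a.x rates overall risk as low.
- **There is a basis for expecting benefit.** Section 3.a cites early mobilisation as reducing complications, 2.a prescribes no activity target, and standard care is unchanged. This makes a low rating reasonable. It does not replace an assessment of the intervention, which 4.d itself calls untested.
- **Other data may fill the gap.** Both arms complete quality-of-life questionnaires, and charts hold many physical events. That is fair, so it would be too strong to say the control arm cannot be used for safety at all. But the protocol does not assign either source to physical harm, as 5.a.vii does for psychological harm. By-arm tables may well sit in an analysis plan that is not shown; which events are asked about, and of whom, is fixed at data collection.

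That recording would in fact be one-sided is a risk created by the wording. Nothing in the protocol shows that it will happen.

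**Conclusion.** The point holds as a cheap and worthwhile improvement. Section 5.a.vi assesses the device only and omits the physical effects of the activity that the intervention aims to increase, although 5.a.vii and 4.d already recognise the feedback as a source of risk and the approach as untested. Detection is scheduled, but under 5.c it depends on attribution, and like-for-like recording in the two Cohort 1 arms is not required.

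The direction of any distortion is uncertain: more events could be recorded in the Watch arm, or events could be lost in both arms. Its size cannot be derived from the protocol, because any figure would only restate assumed event and attribution rates. The conclusion rests on the wording of 5.c and on patients knowing their arm. It does not extend to a by-arm comparison in Cohort 2, which has a single group.

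**What to change.** 1. **Section 5.a.vi:** extend the statement to the activity-feedback intervention, so that it covers possible physical effects of increased mobilisation and agrees in scope with 4.d and 5.a.vii.
2. **Section 5.c, Cohort 1:** replace the wording that depends on attribution with one short fixed list of physical events, asked identically in both arms at the four existing visits, regardless of presumed cause. The investigators should settle the list; candidates are falls, unplanned emergency visits or readmission, reoperation, wound or implant problems, and marked increase in pain. Align 5.d with it.
3. **Reporting:** give counts by randomised arm descriptively, without a formal test.

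The cost is a few minutes per visit and one more table. No visit is added and no treatment changes. The limit is the one shown above: at about 100 per arm the counts can describe the pattern of harms but cannot establish or exclude a moderate excess.

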2. STUDY PROCEDURES

a. Procedures

This study protocol is similar in parts to previously approved protocol, "Accelerometers in spine surgery study," for which [name] (Co-PD on current proposal) is the PD.

All English-speaking adult patients (≥ 18 years old) who are undergoing elective spine surgery (excluding patients with spine trauma, tumors, or infection) for Cohort 1 or are undergoing any back treatment for Cohort 2 by neurosurgery attending physicians at Stanford ([name], [name], [name], [name], [name], [name]) will be eligible for participation in this study.

All participants in Cohort 1 and Cohort 2 will receive our standard of care.

In Cohort 1, percentage for random assignment to each group is 50%. Those assigned to the "intervention" (i.e., the Apple Watch) will receive instructions on how to use the activity section within the Watch. The participants will either have their mobility data submitted via the previously approved app Neurocoach. The intervention group will wear the Apple watch 2-6 weeks pre-operatively as well as at least 6 months post-operatively (may continue to wear as long as 12 months). The control group will not. Patients in the interventional group receiving an Apple Watch may be asked to come in for a training and set-up visit at clinic. Parking passes will be provided for this visit.

All patients in Cohort 1 will be seen in follow-up clinic as per standard of care (4-6 weeks, 3 months, 6 months, and 12 months post-operatively). At each time point, all patients will complete standardized quality of life questionnaires (several of which are already incorporated in our postoperative clinic) and an additional study-specific questionnaire regarding satisfaction with their care and recovery.

In Cohort 2, all participants will receive an Apple Watch and instructions on how to use the activity section within the Watch. The participants will have their mobility data submitted via the previously approved app Neurocoach. Participants will wear the Apple Watch for 2-3 weeks. Participants will complete standardized quality of life questionnaires (several of which are already incorporated in our postoperative clinic) at the beginning and end of the 2-3 week study. This cohort will have their pain monitored daily using brief questionnaires.

b. Procedure Risks

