4. PARTICIPANT POPULATION

a. Planned Enrollment

Cohort 1:

- (I) around 200 patients total at Stanford Neuroscience Health Center and at Stanford Medicine Orthopaedic Spine Center
- (II) around 200 patients total at Stanford Neuroscience Health Center and at Stanford Medicine Orthopaedic Spine Center (the cohort will not include participants from any other non-Stanford sites)

100 patients will be in the control arm - no Apple Watch or app; 100 patients will be in the intervention arm - will receive Apple Watch and will download app.

A few additional subjects may be enrolled so as not to delay the completion of the trial. Surgery for a subject may change to several weeks later or subjects may decide not to do surgery. The target in each cohort will remain at about 100 subjects.

Participants will be adults (greater than or equal to 18 years old) who will be undergoing elective spine surgery at Stanford University Hospital by a Stanford Neurosurgery or Orthopaedic Spine attending physician. The reason for using such participants is to be able to effectively assess long-term mobility and satisfaction outcomes of patients who have undergone spine surgery who will be using Apple Watch in addition to the standard of care.

Cohort 2:

- (I) 15 patients total at Stanford Neuroscience Health Center
- (II) 15 patients total at Stanford Neuroscience Health Center (the cohort will not include participants from any other sites)

Participants will be adults (greater than or equal to 18 years old) who are undergoing any back treatment by a Stanford Neurosurgery attending physician. The reason for using such participants is to be able to effectively assess short-term mobility and satisfaction outcomes of patients experiencing back pain who will be using Apple Watch in addition to the standard of care.

b. Age, Gender, and Ethnic Background

All participants will be adults (greater than or equal to 18 years old). There is no other specification in terms of gender or ethnic background.

c. Vulnerable Populations

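### Cohort 1: the rule in 5.c for unexpected hazards ties stopping the Watch to leaving the study, so hazards caused by the Watch or app cost follow-up forms in the Watch arm only

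*Protocol*

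**What the plan says.** Section 5.c of the Protocol describes in-person check-ins for Cohort 1 at 4-6 weeks and at 3, 6 and 12 months, and "these check-in meetings will include detecting any negative effects of the study on the patient". It then states the consequence: "Any unexpected hazards will be reported to the IRB, and the patient will be removed from the study". The same sentence is repeated for Cohort 2, which has no control arm and is not part of this point.

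Other sections that bear on the rule:

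- **Allocation and exposure.** Cohort 1 is randomised in equal shares (2.a). Section 4.a states that "100 patients will be in the control arm - no Apple Watch or app", and plans another 100 patients with both.
- **Satisfaction form.** At each time point all Cohort 1 patients complete "an additional study-specific questionnaire regarding satisfaction with their care and recovery" (2.a). Objective 4 in 1.b asks: "Are patients more satisfied with their spine care as a result of using the Apple Watch in our practice".
- **Quality of life forms.** Section 2.g says: "All patients will complete the Stanford Spine quality of life questionnaires, as per the standard of care, at all postoperative visits".
- **Foreseen harm.** Section 5.a.vii accepts that activity feedback may have negative psychological effects of unknown degree. It relies on the questionnaires "so we can assess whether the Apple Watch itself is having a detrimental effect on our patients".
- **Expected frequency.** No hazard rate is given. Section 5.a.x rates overall risk as low, and 5.d says that adverse effects are not expected.

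**The concern.** Stopping the device and ending follow-up are different decisions, and 5.c makes them one. In a randomised comparison the loss is one-sided for any hazard that comes from the Watch or app, because only one arm is exposed. Patients removed for such a hazard are plausibly less satisfied than those who stay, so the Watch-arm patients left at later visits could look somewhat better than the arm as randomised.

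This is a rule about conduct, not analysis. A statistical analysis plan can make assumptions about missing forms, but it cannot bring back forms that the protocol stopped collecting. For hazards caused by the Watch or app, stopping their use already ends the exposure, so ending follow-up as well usually adds little protection.

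**Working it through.** The plan states no figure on this point, so there is nothing to reproduce. The check has two parts.

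**1. What a removal costs, form by form**

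| Data | Status in the protocol | After removal |
|---|---|---|
| Forms completed before removal | Not said to be discarded | Kept, as far as the text shows |
| Later satisfaction forms (2.a) | Study-specific, not standard of care | End with removal |
| Later quality of life forms (2.g) | Standard of care at all postoperative visits | Still completed in clinic; whether the study may use them is not stated |

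The clear loss is therefore the later satisfaction forms. A hazard found early costs several of them; one found at the last visit costs few or none.

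**2. How far the Watch-arm mean could move**

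Inputs:

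- n = 100 Watch patients (4.a).
- k = number removed for a hazard caused by the Watch or app. The protocol gives no rate, so k is varied.
- D = how much worse removed patients would have scored than retained ones at a later visit, in SD. This is assumed: 0.5 to 1.

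The mean of all patients is a weighted average:

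mean(all) = (k/n) × mean(removed) + (1 − k/n) × mean(retained)

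With mean(removed) = mean(retained) − D, this gives

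mean(retained) − mean(all) = (k/n) × D

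| k | D = 0 | D = 0.5 SD | D = 1 SD |
|---|---|---|---|
| 1 | 0 | 0.005 | 0.010 |
| 2 | 0 | 0.010 | 0.020 |
| 5 | 0 | 0.025 | 0.050 |
| 10 | 0 | 0.050 | 0.100 |

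For scale, the standard error of the difference between arms is √(1/100 + 1/(100 − k)) SD.

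- k = 1, D = 0.5: SE = √(1/100 + 1/99) = 0.142, and 0.005/0.142 = 0.04 SE.
- k = 2, D = 1: SE = √(1/100 + 1/98) = 0.142, and 0.020/0.142 = 0.14 SE.

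With an assumed two-sided alpha of 0.05, the type I error would be 0.050 in the first case and 0.052 in the second. If patients stop the Watch but stay in follow-up and complete their forms, k = 0 and this source of bias disappears.

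**The case against.** The strongest reply is that the rule will rarely be used, and that its trigger is narrow. It covers only unexpected hazards. The one psychological harm tied to the Watch is foreseen in writing in 5.a.vii and is to be monitored and dealt with. Section 5.d adds that adverse effects are not expected, but can be found at visits and acted on where necessary. Responses short of removal therefore exist. This stands, and it limits the size of the point.

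The documents also show that wearing the Watch and being followed up can come apart. Section 2.a requires at least 6 months of postoperative wear, while visits run to 12 months. This stands too, but it is a wearing schedule. It does not say what happens to a patient with a hazard.

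A third reply is that removal protects patients and should not be weakened. For a privacy breach this is right: continued data collection is itself the exposure, so stopping the Watch would not end it. Such hazards can also occur in either arm. The team's discretion in 4.c to end a vulnerable participant's involvement where appropriate should also be kept. Any change must therefore be limited to hazards caused by the Watch or app and must carry a safety exception.

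A reader might infer that 5.c removes the very patients whom 5.a.vii wants measured. That follows only if the foreseen psychological effects count as unexpected, which is the less natural reading. If they are read as expected, there is no conflict.

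**Conclusion.** The point holds in a limited form. For an unexpected hazard caused by the Watch or app, 5.c removes a randomised patient from one arm only and ends the later satisfaction forms that bear on objective 4. The likely size is a shift of 0.005 to 0.02 SD for 1 or 2 removals among 100. This assumes that removed patients differ by 0.5 to 1 SD; with no removals, or no difference, it is zero.

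Two stronger readings are not supported:

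- **That the bias could be material.** A shift of 0.05 to 0.10 SD needs 10 removals at the assumed differences, and the protocol gives no reason to expect that many. Assuming that the worst-scoring patients are the ones removed would give more, but the rule is triggered by hazards, not by low scores.
- **That the quality of life comparison is lost.** Those forms continue as standard of care. What is open is whether the study may use them after removal.

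Severity is minor. The case for a change rests on its low cost and on the fact that forms never collected cannot be recovered, not on a large bias.

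**What to change.** Change the Cohort 1 sentence in 5.c only, for example to:

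> Every unexpected hazard is reported to the IRB. If it is caused by the Watch or app, their use is stopped and the patient stays in the study in the assigned group, with the scheduled visits and questionnaires, unless he or she withdraws consent or the investigator or IRB judges that continued participation is itself a risk. For other unexpected hazards, such as a privacy breach, the patient is removed.

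The Cohort 2 sentence stays as it is, and IRB reporting is unchanged. No visits or forms are added: the clinic visits and quality of life forms are standard of care (2.a, 2.g), and the satisfaction form is already scheduled for all Cohort 1 patients (2.a). The downside is that an affected patient is asked to keep completing questionnaires, a small burden that he or she can end by withdrawing.
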